Basic Study Information

1. * Title of study:

AAT + tDCS to reduce cue-induced craving and smoking behavior

2. * Short title:

AAT+tDCS

3. * Brief description:

Smokers are highly reactive to smoking-related stimuli and report that this cue reactivity (CR) is a major obstacle to quitting. To date, no pharmacologic methods attenuate CR, and attempts to diminish it with traditional cue exposure treatment (CET) have not proven effective. The proposed study will test a highly novel cue-based smoking treatment adjunct combining an Approach/Avoidance Task (AAT) with brain stimulation via tDCS applied to the dorsolateral prefrontal cortex (dlPFC) during personalized multi-cue exposure; the goal of which is to discover an effective means of reducing cue reactivity and daily smoking, and increasing intent and confidence to quit, among high treatment-interest smokers.

4. * What kind of study is this?

Single-site study

5. * Will an external IRB act as the IRB of record for this study?

Yes No

6. * Local principal investigator:

[name]

Name	Description
------	-------------

There are no items to display

3. Have you, [name], verified that all members of the research team have the appropriate expertise, credentials, training, and if applicable, child clearances and/or hospital privileges to perform those research procedures that are their responsibility as outlined in the IRB application?

* Yes No

Study Scope

Check all that apply

1. * Will this study actively recruit any of the following populations?

- Adults with impaired decision-making capacity
- Children (under the applicable law of the jurisdiction in which the research will be conducted (<18 years for PA))
- Children who are Wards of the State
- Employees of the University of Pittsburgh/UPMC
- Medical Students of University of Pittsburgh as primary research group
- Students of the University of Pittsburgh
- Neonates of uncertain viability
- Non-viable neonates
- Non-English speakers
- Nursing home patients in the state of Pennsylvania
- Pregnant women
- Prisoners
- N/A

2. * Will any Waivers be requested?

- Waiver/Alteration of Consent
- Waiver to Document Consent
- Waiver/Alteration of HIPAA
- Exception from consent for emergency research
- N/A

3. * Will this study involve any of the following?

- Specimens
- Honest Broker to provide data/specimens
- Return of Results to Subjects or Others
- Fetal tissue
- N/A

4. * Will Protected Health Information be collected?

- Pitt medical records
- UPMC medical records
- Other Institutions' medical records
- N/A

5. * Other Requests?

- Deception (if not Exempt, also requires Waiver/Alteration of Consent)
- Emergency Use / Single Patient Expanded Access (using FDA Form 3926)
- Placebo Arm
- Withdraw from usual care
- N/A

6. * Determining Scientific Review:

WPIC SRC - Western Psychiatric Institute and Clinic Scientific Review Committee
(this option MUST be picked if from Department of Psychiatry)

7. * Has this study (or substantially similar study) been previously disapproved by the Pitt IRB or, to your knowledge, by any other IRB?

- Yes
- No

Review the [HRPO policy](#), if participating in research at the VA Pittsburgh Healthcare System or using funding from the VA

8. * Does the study use an approved drug or biologic, use an unapproved drug or biologic, or use a food or dietary supplement to prevent, diagnose, cure, treat, or mitigate a disease or condition?

Yes No

9. * Does the study evaluate the safety or effectiveness of a device (includes in-vitro laboratory assays)?

Yes No

10. * Is this application being submitted to convert an approved study from OSIRIS to PittPRO? ([Tip Sheet](#))

Yes No

11. * Does your research protocol involve the evaluation or use of procedures that emit ionizing radiation and, after reviewing this [HUSC guidance](#), does your research protocol require HUSC review? (If yes, upload the [HUSC form](#) in the Local Supporting Documents section). If you are unsure of review requirement, select yes.

Yes No

Research Sites

1. Choose all sites that apply:

University of Pittsburgh
UPMC

*** Select the University of Pittsburgh sites where research will be conducted:**

Main Campus – Pittsburgh

List university owned off-campus research sites if applicable:

*** Select the UPMC sites where research will be conducted:**

Western Psychiatric Institute & Clinic

2. Describe the availability of resources and the adequacy of the facilities to conduct this study:

Western Psychiatric Hospital (WPH) formerly Western Psychiatric Institute and Clinics (WPIC). A dual entity, WPH is the academic Department of Psychiatry within the University of Pittsburgh School of Medicine, and also a psychiatric hospital within the University of Pittsburgh Medical Center (UPMC). This dual status allows for optimal integration between the academic and clinical domain. WPH is recognized nationally and internationally as one of the premier research and treatment centers in the United States. The Department has over 200 primary faculty trained in a mix of disciplines including medicine, psychology, basic sciences, and social work, who are dedicated to the pursuit of excellence in research, training and provision of clinical care. Their efforts are supported by numerous emeritus, secondary, adjunct and volunteer faculty. The intellectual resources at WPH are enriched by close collaborative ties with numerous other Departments within the University of Pittsburgh including Psychology, Neuroscience, Neurology, Kinesiology/Sports Medicine and Radiology. The Department also maintains active collaborations with many other departments and research institutions in the U.S. and around the world. The Department of Psychiatry has been ranked first among all Departments of Psychiatry in the U.S. with regard to research funding from the National Institutes of Health (NIH) since the mid-1980s. The University of Pittsburgh ranks among the top ten universities nationwide in the level of funding from the National Institutes of Health (NIH) <http://www.pitt.edu/research.html>. Founded in 1787, it is one of the oldest institutions of higher education in the United States. As one of the nation's distinguished comprehensive universities, the resources of the University contribute to the intellectual, economic, and social enrichment of Pennsylvania and the nation. The University's mission is to provide high-quality undergraduate programs; offer superior graduate training; engage in research, artistic, and scholarly activities that advance learning through the extension of the frontiers of knowledge and creative endeavor; and cooperate with industrial and governmental institutions to transfer knowledge in science, technology, and health care. Due to its central location on the University of Pittsburgh campus, the Main WPH building is an easily accessed and familiar location for research participants. Most city bus lines stop within a block of this building, and campus shuttles stop directly in front of it. For individuals who choose to drive to research sessions, free parking is easily available in the building's off-street garage.

Devices

1. * List each device in the study that will be evaluated for safety or effectiveness:

Device	Purpose	Type
View NeuroConn DC- Stimulator	An IDE application (G150197) was submitted to the FDA on August 14 (received by the FDA on September 9, 2015). The FDA has determined that the proposed study is a nonsignificant risk device study because it does not meet the definition of a significant risk (SR) device under §812.3(m) of the Investigational Device Exemption (IDE) regulation (21 CFR 812). The letter from the FDA is attached under the "other attachments section". Overall, there are no significant risks associated with tES as all risks are very unlikely and minimally serious. Several investigators have examined the safety aspects associated with transcranial direct current stimulation (tDCS). For example, Iyer et al. (2005), applied 1 and 2 mA anodal, cathodal, and sham DC stimulation to the left prefrontal cortex for 20 minutes while clinical EEG was recorded. Participants were encouraged to report any discomfort or subjective sensations while undergoing stimulation. These researchers observed no aversive EEG abnormalities resulting from DC stimulation, and no participants asked to stop the study or reported any significant discomfort. Differences in mood between sham and stimulation were assessed using the Visual Analog Mood Scale (VAMS) that measures subjective reports of anger, anxiety, confusion, energy, fright, happiness, sadness, tension, and tiredness. The investigators found no measurable effects of stimulation on participants' VAMS scores. Based on their findings, they conclude that limited exposure to direct current stimulation between 1 and 2 mA is a safe procedure in healthy participants. In another study conducted by Gandiga, Hummel, and Cohen (2006), tDCS and sham were compared in healthy volunteers and chronic stroke victims. Discomfort was measured using a 10 point scale, where 1 represented no discomfort and 10 represented extreme discomfort and pain. These researchers report transient and mild discomfort of sensations (12 on the 10 point scale) that weren't significant between sham and stimulation conditions, nor between healthy volunteers and stroke victims. Safety and tolerability of tES has also been examined in adults with schizophrenia (Brunellin et al., 2014), as well as childhood onset schizophrenia (Matai et al., 2011). tES in these studies was well tolerated by participants, and no adverse events were reported. Recently, safety of other forms of tES have been thoroughly examined. Chaieb et al. (2014) examined assessed safety aspects of Sinusoidal transcranial alternating current stimulation (tACS) by measuring neuronspecific enolase (NSE) levels, examining electroencephalogram (EEG) traces and analyzing anatomical data by using magnetic resonance imaging (MRI). tACS was delivered at 5 kHz applied for 10 min at 1 mA intensity over the hand area of the primary motor cortex. No changes were detected in NSE levels, no structural alterations were observed in the anatomical scans and no pathological changes were found in the EEG recordings. Additionally, Zaghi et al. (2010) administered various behavioral and neuropsychological tests during tACS. tACS was not associated with any cognitive adverse effects and had no harmful effects on motor function (Purdue Pegboard Test, Finger Tapping Test). Moreover, tACS was not associated with pain, mood, or anxiety. DCSTIMULATOR has a Maximum Voltage Limitation of +/- 20V. The output circuit of the constant current source of the DCSTIMULATOR is equipped with an electrical fuse which limits the current to 5 mA. Therefore, in any faulty condition and during normal operation, the fuse will become open circuit if the current exceeds 5 mA by a significant amount. The higher the current exceeds 5 mA the faster it will become open circuit. This means that it is impossible for the participant to receive a harmful level of current, even in cases of equipment malfunction. To avoid thermal discomfort and possible skin damage, the German authority (Bundesanstalt für Arzneimittel und Medizinprodukte) gives a limit of 0.1 mA/cm ² for DC current applications. The largest current density we will use here is 0.08 mA/cm ² . We will monitor participant discomfort throughout the administration of tES. If at any point the participant reports perceived heat, tingling, or itching at the site of the electrodes as 8 or higher on a 10 point scale, tES will be stopped immediately. The Co-I, [name], has administered tES to over 250 research participants in previous studies at the University of New Mexico, with only two adverse events, one of which was due to latex allergy, and the other was due to small electric shock caused by suboptimal equipment. Only the PI and trained research staff /Co-I's will administer tES here, and individuals with latex allergy will be excluded. The Neuroconn stimulator used here is robust, so we do not anticipate this to be a problem here.	Abbrevia

+++++++++++++++++++++ Evidence of efficacy across past work, including some from our research team include the following: Past work has shown that brain stimulation with tDCS during CR further enhances cognitive training, as cognitive effects of tDCS are largely dependent upon the cognitive faculty being engaged at the time of stimulation (Bradnam, Stinear, Lewis, & Byblow, 2010). We found enhancement of alerting attention network function measured by the Attention Networks Test, a measure of proactive cognitive control, more than an hour after anodal tDCS directed at right inferior frontal gyrus (Falcone, [name], Clark, & Parasuraman, 2012). tDCS was paired with complex object detection training, which is thought to engage cognitive control networks in the brain. Further, tDCS directed at right frontal cortex has been used to increase reactive cognitive control in the stop-signal task (SST) as evidenced by reaction time and neurophysiological measures obtained with electroencephalography (EEG)(Jacobson, Ezra, Berger, & Lavidor, 2012). Thus, we plan to use CR + tDCS as a means of further enhancing cognitive control among smokers with schizophrenia. Three tDCS studies(Boggio et al., 2009; Fregni et al., 2008; Grundey et al., 2012) in healthy non-quitting smokers (randomized, active vs. sham 1-5 training days) targeting the dorsolateral prefrontal cortex (DLPFC) found dose dependent reductions in cue-induced craving and smoking behavior. tDCS has also been shown to significantly enhance the ability of smokers to resist the urge to smoke(Falcone et al., 2016). Our recent pilot study (N=6) found that weekly group sessions of 30 minutes of mindfulness + tDCS of the right IFG, followed by 60 minutes of mindfulness + counseling led to a significant 50% reduction in cigarettes per day at the end of treatment (d=0.50; Witkowitz et al., 2015). However, CR will be used in this present study, not mindfulness, as it targets multiple aspects of cognition, and has shown greater efficacy to enhance cognitive deficits among patients with psychosis (d=>1(Hogarty et al., 2004) vs. d=.41 (Khoury, Lecomte, Gaudiano, & Paquin, 2013)respectively).

Boggio, P. S., Liguori, P., Sultani, N., Rezende, L., Fecteau, S., & Fregni, F. (2009). Cumulative priming effects of cortical stimulation on smoking cue-induced craving. *Neuroscience Letters*, 463(1), 82–86.
<https://doi.org/10.1016/j.neulet.2009.07.041>

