2. AAT + sham tDCS
3. AC + tDCS
4. AC + sham tDCS

The components of these groups are defined as:

- Approach/Avoidance Task (AAT): The participant will use a joystick to push and pull images in different directions on a computer screen.
- Transcranial Direct Current Stimulation (tDCS): is used to slightly change the way the brain works for a short time. One wet, thin sponge is placed on the participants head and another wet thin sponge is placed on their arm and connected to electrodes which will deliver a very weak electrical current. Before stimulation, their head and arm will be checked for any redness, irritation, or recent shaving of the head. If any of these are seen, we will exclude them from the study. Some participants may feel a slight painless tingling as the current begins, but the tingling should go away after a short time. tDCS will be given at 2.0 mA and stimulate the

dorsolateral PFC (dIFPC) the sham tDCS will be given at 0.01 mA. We will ask the participant at the beginning of and throughout the stimulation to report how much tingling they are feeling on a scale of 1 being "not at all" and 10 being "extreme". If at any point they are experiencing extreme discomfort, we will end the stimulation.

- Active Control (AC): The participant will assess the orientation of a picture and indicate it with a key press.
- Sham tDCS: Two wet, thin sponges are placed on the participants head and arm and the sponges will be connected to electrodes just as the actual tDCS but they will not deliver any electrical current.

Visits 2 and 9: During this visit the participant will have an attentional bias assessment while undergoing an electroencephalography (EEG).

- Attentional-Bias: You will be seated in front of a computer with a four-button color response box. Four different word lists of 15 words each will be presented in a random order with no repeats. For each trial, a cross appears in the center of the screen followed by one word from the list in one of four colors. You will press the button that matches the color in which the word appears.

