	Infrequent Risks	The risk associated with transcranial electrical stimulation is minimal. There is a small risk of skin irritation which is minimized by using saline water as the conductive medium, and through the monitoring of participant discomfort throughout the procedure. tDCS is seen as a non-invasive medical procedure, and the commonly reported side-effects in active vs. sham treatments are itching (39.3% vs 32.9%), tingling (22.2% vs 18.3%), headache (14.8% vs 16.2%), burning sensation (8.7% vs 10%), and discomfort (10.4% vs 13.4%). ¹⁰⁷ Redness at the electrode site has also been reported.
	Other Risks	No Value Entered

View	Research Activity	Cue-Reactivity
	Common Risks	Some of the stimuli used have been shown to significantly increase urge to smoke. The discomfort of increased urge to smoke is anticipated to dissipate fairly quickly, and over the course of the treatment may lead to less robust responses.
	Infrequent Risks	No Value Entered
	Other Risks	No Value Entered

View	Research Activity	Collection and storage of private information
	Common Risks	No Value Entered
	Infrequent Risks	There is a rare possibility of a breach of confidentiality, but we have safeguards in place to minimize that. All records related to your involvement in this research study will be stored in a locked file cabinet and all electronic records are password and firewall protected. Your identity on these records will be indicated by a case number rather than by your name, although we may use your initials on certain forms.
	Other Risks	No Value Entered

2. * Describe the steps that will be taken to prevent or to minimize risks:

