The Neucoconn DC Stimulator Plus used in this study will be routinely tested (monthly) to ensure that the current and voltage delivered by the device are as expected based on the settings applied. We will test these parameters using a standard multimeter (Fluke), and electronic logs of these tests will be maintained by the PI. Potential risk of skin irritation from transcranial DC stimulation is minimized by using saline water as the conductive medium, through the monitoring of participant discomfort throughout the procedure, and by discontinuation of the procedure if significant discomfort is experienced by the participant. Confidentiality and loss of Privacy. Information on research participants will be protected for confidentiality similar to medical records, and will be kept separate from the research binders in locked metal cabinets and for authorized access only. No

identifiable data will be made available while compiling the study report or when preparing the eventual results for a journal article. If the cue reactivity or questionnaires cause the participant discomfort they do not have to answer the questions and may stop the study at any time.

3. Financial risks - will the subject or insurer be charged for any research required procedures?

Yes No

4. Describe the steps that will be taken to protect subjects' privacy:

All research procedures will be completed in a private room and with only the research staff present.

5. What steps will be taken in the event that a clinically significant, unexpected disease or condition is identified during the conduct of the study:

The PI's would consult with the subject and refer to the appropriate physician for follow-up.

6. Describe the potential benefit that individual subjects may experience from taking part in the research or indicate if there is no direct benefit. Do not include benefits to society or others:

There isn't a direct benefit to the participant for participating in this study; however, it's possible they may find the study procedures helpful to their urge to smoke.

7. Do you anticipate any circumstances under which subjects might be withdrawn from the research without their consent?

Yes No

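### The rule stopping tDCS at a rating of 8 covers heat, tingling and itching, but the described procedure prompts a rating of tingling only

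*Combined protocol and SAP*

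**What the plan says.** Three sections deal with stopping stimulation.

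- **Devices, item 1 (NeuroConn DC-Stimulator).** This section promises general monitoring: "We will monitor participant discomfort throughout the administration of tES". It then sets a numeric stop for heat, tingling or itching: "itching at the site of the electrodes as 8 or higher on a 10 point scale, tES will be stopped immediately".
- **Research Activities, item 1 (description of tDCS).** Staff ask, at the start of stimulation and throughout, how much "tingling they are feeling on a scale of 1 being 'not at all' and 10 being 'extreme". The stop is then worded without a number: "If at any point they are experiencing extreme discomfort, we will end the stimulation".
- **Risk and Benefits, item 2.** Skin irritation is to be limited partly by "discontinuation of the procedure if significant discomfort is experienced by the participant". No number and no particular sensation is given.

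No section of the supplied text describes a prompted rating of heat or itching.

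**The concern.** A numeric stop needs a number to act on. The procedure obtains one for tingling. For heat and itching, staff learn the score only if the participant offers it or if general monitoring leads them to ask. Stimulation runs while the participant is working at the joystick task or the control task during cue exposure. My inference, which the plan does not state, is that a direct question is more dependable then than a spontaneous report.

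The two unprompted sensations matter on the document's own account. The current-density limit in the device section is introduced with the words "To avoid thermal discomfort and possible skin damage", so heat is worth asking about. The risk table in Risk and Benefits, item 1, gives, for active versus sham, "itching (39.3% vs 32.9%), tingling (22.2% vs 18.3"%), so itching is reported more often than the one sensation that is prompted.

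What is at stake is participant comfort and skin safety during stimulation. No endpoint or test is affected.

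**Working it through.** The plan states no figure to reproduce, so the check is mainly a comparison of the sections.

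**1. Rule against prompt, by sensation**

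| Sensation | Stop at 8 or higher (Devices, item 1) | Prompted 1–10 rating (Research Activities, item 1) |
|---|---|---|
| Tingling | yes | yes |
| Heat | yes | none described |
| Itching | yes | none described |

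The rule has a prompted input for 1 of 3 sensations. Even for tingling, the procedure does not restate the cut-off of 8, so staff must take it from the device section.

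**2. Whether the stop wordings conflict.** They do not. Staff can stop at a rating of 8 or higher on any of the three sensations, and also stop for discomfort described as extreme or significant. The discomfort stops add to the numeric rule and cannot delay it.

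**3. Sessions involved.** The power section gives 20 participants in each of 4 groups, and the design gives 5 intervention sessions.

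- Active: 20 × 2 groups × 5 = 200 sessions, before replacement of dropouts.
- Sham: 20 × 2 groups × 5 = 200 sessions, at a stated 0.01 mA against 2.0 mA active. The ratio is 2.0 / 0.01 = 200, so the safety question lies mainly in the active sessions.

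**4. How often the sensations occur.** The rates are those in Risk and Benefits, item 1, active versus sham:

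- Itching: 39.3% − 32.9% = 6.4 points higher on active.
- Tingling: 22.2% − 18.3% = 3.9 points higher on active.
- Burning, taken here as an assumption to be the closest listed symptom to heat: "burning sensation (8.7% vs 10"%), that is 8.7% − 10% = −1.3 points, lower on active.

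These rates carry no severity. The number of ratings of 8 or higher cannot be derived from them and is probably small.

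**5. Other safeguards.** The largest planned density is 0.08 mA/cm² against a cited limit of 0.1 mA/cm², and 0.08 / 0.1 = 80%. The stimulator is fuse-limited, trained staff give the stimulation, and adverse events are monitored at each laboratory visit (Data Safety and Monitoring, item 1).

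**The case against.** The strongest reply is that the device section already governs. It belongs to the same application, it promises monitoring throughout, and a report on a 10-point scale presupposes that participants have been given that scale for each sensation. The procedure section is a summary partly in participant-style language, so its silence on two sensations may be brevity. Research Activities, item 2, exempts case report forms from upload, so a session log that asks about heat and itching may exist unseen. All of this stands. It limits the point to a missing prompt in the described procedure. It does not remove the point, because that section is asked for enough detail to judge risk and is the only place where ratings during stimulation are described.

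A reader might go further in two ways that the documents do not support.

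- **That the procedure lets staff wait until 10.** The word extreme labels 10 on the tingling scale, so 8 and 9 might look like a gap between the two rules. But the stop sentence in the procedure concerns discomfort, which has no scale there, and the cut-off of 8 still applies to tingling.
- **That monitoring of heat and itching is absent, or that the sections contradict each other.** General discomfort monitoring is promised, and all three stop wordings can be followed together.

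The evidence of harm is also thin. The burning rate is lower on active than on sham. The device section cites a study using a 10-point scale in which discomfort was mild and did not differ from sham, and it reports the FDA's determination of nonsignificant risk. That keeps the point minor.

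**Conclusion.** The point holds as a cheap improvement. The plan commits to a numeric stop on three sensations, and the described procedure prompts a rating for one of them without restating the cut-off. For heat and itching the rule depends on general monitoring and unprompted reports.

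The residual risk is low and power, alpha and endpoints are unaffected. The conclusion rests on the supplied text being the full account of what staff ask during stimulation. If a session form already asks for all three sensations, what remains is a sentence in the procedure saying so and giving the cut-off.

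**What to change.** In Research Activities, item 1, ask for heat, tingling and itching on the same 1 to 10 scale, at the start of and throughout stimulation, in active and sham sessions alike. State there that stimulation stops at 8 or higher on any of the three.

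Keep the procedure's stop for extreme discomfort and the participant's right to stop as additional criteria. In Risk and Benefits, item 2, add the numeric rule beside the existing stop for significant discomfort and do not replace that wording. It also covers headache, burning and general discomfort, which the three-sensation rule does not name, so replacing it would narrow protection.

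The cost is two more short ratings at each check and small wording changes in two sections. The downside is slightly more interruption of the joystick or control task, the same in every group if the questions are asked identically. No visit is added and the sample size does not change. If session forms exist, they should be checked for agreement with the revised text.
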